9.8 Management of Dry Eye Symptoms During Follow-Up

During follow-up, if subjects require drops to relieve their dry eye symptoms, they may use Refresh® Plus lubricant vials which have been supplied by the investigator. Other types of over-the-counter lubricants should not be used. Subjects should bring the unused vials to each follow-up visit so that they can be counted.

Subjects should not use Restasis or Xiidra during the study. Use of these drugs will result in the subject being excluded from the "Per Protocol" analysis from the time of initiation of these drugs forward.

Subject should not be treated with other dry eye treatments (e.g. LipiFlow, punctal plugs, etc.) during the course of the study. Administration of these treatments will

result in the subject being excluded from the "Per Protocol" analysis from the time of initiation of these treatments forward.

NOTE: If a subject had a punctal plug at the baseline visit and it falls out during the study, it should be replaced.

9.9 WITHDRAWAL AND DISCONTINUATION

All subjects have the right to withdraw at any point during the treatment without prejudice. The investigator can discontinue any subject at any time if continued participation in the study would result in harm to the subject. All efforts should be made by the investigator to retain the subject in the study. If a subject withdraws prematurely from the study, a genuine effort must be made to determine the reason(s) the subject discontinued the study. The reason must be recorded in the subject's file and on the Study Exit Form.

If a subject withdraws from the study post-randomization but prior to receiving the TearCare or Warm Compress treatment, then that subject may be replaced in the study by a newly enrolled subject.

9.10 SUBJECTS LOST TO FOLLOW-UP

Subjects who do not show up for a follow-up must be contacted to attempt to have them come for the follow-up. For those subjects who cannot be reached, at least 3 phone call attempts should be made and documented. If still no response, a registered letter shall be sent to the address on file for the subject in an attempt to make contact. If a subject misses two consecutive follow-up visits without any contact with the study staff, the subject will be considered lost-to-follow-up unless there is a further communication by the subject.

10 Adverse Events (AEs)

Adverse Events are defined below. Adverse events that occur in the eye during the trial, whether they are considered to be device related or not, must be documented in the subject's records. Date of the event, its severity, treatment (if any) and the assessed relationship of the event to the study device will be recorded on the Adverse Event Form. Conditions which exist at the time the subject is enrolled do not need to be recorded as adverse events unless they increase in severity during the study.

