6.2 SAFETY ENDPOINTS

Safety will be assessed by evaluating the following measures over time:

- Device-related adverse events (all adverse events will be recorded)
- Best corrected visual acuity (ETDRS)
- Intraocular pressure (IOP)
- Discomfort/pain during treatment

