10.1 DEFINITIONS OF AE, SAE, SADE, USADE

Adverse Event	Any untoward medical occurrence in a subject who has been treated with the device that does not necessarily have causal relationship with the treatment.
Adverse Device Effect	Any unfavorable and unintended sign (including an abnormal laboratory finding), symptom, or disease that is possibly related to the study device.
Serious Adverse Event (SAE)	Any untoward medical occurrence that: Results in death Is life-threatening Requires in-patient hospitalization or prolongs existing hospitalization Necessitates medical or surgical intervention to preclude permanent impairment of a body function or permanent damage to a body structure Sight threatening
Unanticipated Adverse Device Effect	Any serious adverse effect on health or safety, any life-threatening problem or death caused by, or associated with a device if that effect, problem, or death was not previously identified in nature, severity, or degree of incidence in the clinical investigational plan; or any other serious problem associated with a device that relates to the rights, safety, or welfare of subjects (21 CFR 812.3(s)). Any sight-threatening event, whether listed in the protocol or not, is considered to be reportable as a UADE

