10.2 LIST OF ANTICIPATED POTENTIAL ADVERSE EVENTS

Anticipated potential adverse events include those that might reasonably be expected to occur in this study because they are associated with dry eye disease, the risk analysis for TearCare System (albeit remote likelihood), study testing methods or potential risks associated with warm compresses and lid massage.

- Burn, erythema, or swelling of the eyelids
- Conjunctival injection (Moderate or severe)
- Conjunctival abrasion
- Corneal abrasion
- Corneal deformation
- Allergic or inflammatory reaction to medical adhesive on the iLid device

- Formation of a chalazion or stye
- Loss in BCVA of 2 lines or greater
- Worsening of dry eye symptom
- Increased discomfort or pain of ocular surface (grittiness, foreign body sensation, etc.)
- Discomfort or pain of eyelids or orbit

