10.3 REPORTING ADVERSE EVENTS AND UNANTICIPATED ADVERSE DEVICE EFFECTS

Identification, collection and reporting of adverse event information is the responsibility of the principal investigator. The investigator records the date of the event, its severity, treatment (if any) and the assessed relationship of the event to the study device on the Adverse Event Case Report Form (AE CRF).

Any ocular-related **serious adverse event** (SAE) should be reported to the study sponsor within one working day of learning of the event. Non-ocular-related SAEs should be reported to the study sponsor within two working days of learning of the event. Email the AE CRF to [contact].

Any unanticipated adverse device effects (UADE) must be reported to the following two entities:

- The study sponsor Within one working day of the investigator first learning of the event, e-mail the AE CRF to [contact]; and
- 2. The reviewing IRB As soon as possible, but no later than 10 working days after the investigator first learns of the event, report per the IRB's instructions.

The sponsor will conduct an evaluation of unanticipated adverse device effects. If the sponsor determines that an unanticipated adverse device effect presents an unreasonable risk to subjects, parts of the investigation presenting risks will be terminated. Termination will occur no later than 5 working days after the sponsor makes such a determination and no later than 15 working days after the sponsor first received notice of the effect.

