11.5 Possible interactions with concomitant medical treatments

It is anticipated that there will be no interactions with concomitant medical treatments.

11.6 Steps that will be taken to control or mitigate the risks.

The major risks to the subjects and the steps taken to control or mitigate them are described below:

1. Overheating of the eyelids: All TearCare treatments will be done in the investigator's office under direct supervision of the investigator. The device delivers heat to the eyelids at a temperature ranging from 41-45°C. This temperature range was selected because it is both safe for eyelid heating and

effective for melting obstructions in the meibomian glands.^{48,49,50,51} The user can adjust the temperature up or down to a level that is comfortable, and may also shut off the System at any time if it is too uncomfortable or painful. In addition, the TearCare System continuously monitors and regulates the temperature at the tissue-contacting surface of the iLid devices and has been designed to not exceed the maximum allowable temperature.

- 2. Corneal abrasion: If the iLid devices are not positioned properly or come loose during the treatment, there is the potential for a corneal abrasion. To mitigate this, the supervising physician will apply the strips to the subject and will monitor their position during the treatment to ensure they remain in place and secure.
 - In addition, there is the possibility of corneal abrasion or abrasion of the eyelid surface during expression of the meibomian glands. To reduce the chance of abrasion, the forceps have been designed with smooth surfaces (i.e. no rough edges) and only trained users will perform expression.
- Worsening of dry eye symptoms: It is possible that subjects will experience a
 worsening of dry eye symptoms during the study. Subjects will undergo a
 complete eye exam at each visit and if any untoward or worsening signs of
 ocular surface disease are observed, they will be treated appropriately.

In addition to the above, the following mitigation steps have also been taken to reduce the risks in this study:

- The device has been tested to demonstrate that it meets performance and safety specifications, as described in Section 5.1.
- Instructions for Use are provided with each device.
- The clinician using the device will be trained in how to safely and correctly apply and remove the iLid devices, and operate the TearCare System.

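### Causality is recorded only against the study device, so the device-related adverse event endpoint is zero by construction in the control arm before crossover and cannot compare the safety of the two treatments

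*Combined protocol and SAP*

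**What the plan says.** The first safety endpoint in section 6.2 is "Device-related adverse events (all adverse events will be recorded". The objective in section 2 is comparative: safety and effectiveness of TearCare against daily compress and massage.

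Causality appears in two places, each with one reference point. The introduction to section 10 says that "the assessed relationship of the event to the study device will be recorded on the Adverse Event Form". Section 10.3 has the investigator record the "assessed relationship of the event to the study device on the Adverse Event Case Report Form (AE CRF". Section 10.1 defines an adverse device effect as a sign, "symptom, or disease that is possibly related to the study device". The synopsis names the study device as the TearCare System. No section provides for relatedness to gland expression, to compress and massage, or to the study's examinations.

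The plan nevertheless recognises those sources of harm. Section 10.2 draws its list of anticipated events partly from "potential risks associated with warm compresses and lid massage" and from the study tests. Section 11.6 says that "there is the possibility of corneal abrasion or abrasion of the eyelid surface during expression of the meibomian glands".

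Two definitions are also framed around the device. Section 10.1 defines an adverse event as "Any untoward medical occurrence in a subject who has been treated with the device", and section 12.1 makes subjects evaluable for safety if TearCare was attempted on them. Section 12.5.9, by contrast, reports all adverse events by treatment group and category.

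**The concern.** A comparative safety objective needs a measure that can take a non-zero value in both arms. The first-listed endpoint cannot. A lid burn from a compress in a control subject is a treatment harm, but before crossover it is not related to a device that the subject has never received.

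The all-event tables are the fallback, but they mix treatment harms with worsening dry eye and test-related events, all of which 10.2 anticipates. Relatedness that is not recorded at the time is hard to reconstruct afterwards.

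A second, smaller problem is in the TearCare arm. Expression with the forceps is part of the treatment, but the plan does not say whether the forceps are part of the study device. With up to 15 centers (7.3), the same abrasion could be attributed differently from site to site.

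**Working it through.** **1. The plan's own safety figures.** Section 23.2.3 takes n = 100 and a true rate of 0.01.
- Chance of at least one event: 1 − (1 − 0.01)^100 = 0.634, as stated.
- One-sided 95% upper limits by the Wilson score method: 0.0263 for 0/100 and 0.0436 for 1/100, matching the stated 0.026 and 0.044. Exact (Clopper-Pearson) limits would be 0.0295 and 0.0466.

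The figures reproduce. None depends on how events are attributed, so they neither support nor refute the point.

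**2. Control arm, from the text.** The endpoint counts events related to the study device. The study device is the TearCare System. Control subjects do not receive it before the crossover described in 12.5.8. The control count up to then is therefore 0 whatever the true rate of compress harm.

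**3. What a structural zero does (illustration).** Assume 100 per arm (12.7), the same true treatment-related rate p in both arms, and every TearCare event counted as device-related. Expected counts are 100p against 0 under device-only attribution, and 100p against 100p under attribution to assigned treatment. With control fixed at 0/100, a two-sided Fisher test gives p = 0.059 at 5 events and 0.029 at 6, so the chance of p < 0.05 is P(X ≥ 6) for X ~ Binomial(100, p).

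| Rate p, both arms | Expected, device-only | Expected, both counted | P(Fisher p < 0.05), device-only | P(Fisher p < 0.05), both counted |
|---|---|---|---|---|
| 2% | 2 v 0 | 2 v 2 | 1.5% | 0.5% |
| 5% | 5 v 0 | 5 v 5 | 38% | 2.1% |
| 10% | 10 v 0 | 10 v 10 | 94% | 2.9% |

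The visible plan specifies no between-arm safety test, so the Fisher column only gauges how misleading the 5 v 0 contrast would be.

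**4. TearCare arm (illustration).** If a share s of TearCare events came from expression and were scored as not device-related, the chance of seeing at least one device-related event in 100 would be 1 − (1 − p(1 − s))^100. At p = 0.01:
- s = 0: 0.634
- s = 0.25: 0.53
- s = 0.50: 0.39
- s = 0.75: 0.22

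The documents give no value for s.

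**5. Are the forceps part of the device?**
- Towards yes: 4.3 (device description) covers expression; 7.1 includes it in TearCare treatment; 11.2 takes the 10.2 list, which contains corneal and conjunctival abrasion, as the anticipated effects of the System; 11.6 relies on forceps design to limit abrasion; and a possible relationship is enough under 10.1.
- Towards no: 7.1 describes a session with the System followed by expression with forceps; 9.7 names TearCare treatment and gland expression as separate acts; 11.3 describes a removable, non-invasive heating device.

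The balance leans towards counting expression abrasions, but the boundary is never stated.

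**6. Definitions against analysis.** Read literally, 10.1 and 12.1 exclude control subjects until they cross over. Section 12.5.9 needs them in the tables from the start. These cannot all hold.

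**The case against.** The strongest reply is that harm data are preserved. Section 6.2 says that all adverse events are recorded, section 10 requires ocular events to be documented regardless of device relationship, and 12.5.9 tabulates them by arm. Visual acuity, IOP and discomfort or pain are further safety endpoints, and 9.5.5 collects discomfort in the compress arm too. A zero in the control arm is simply what device-related means, and the planned safety analysis is descriptive. All of this stands, and it limits the consequence to one endpoint. It does not make that endpoint comparative.

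Three stronger readings are tempting, and the documents do not support them.
- A reader might infer that compress burns and forceps abrasions disappear from the safety record. They do not, for the reasons just given.
- A reader might infer that expression abrasions fall outside the endpoint. The text leans the other way; what is established is only that the answer is left to each investigator.
- A reader might take the 23.2.3 calculation (63%, 87% and 99% at rates of 1%, 2% and 5%) as the chance of misattribution. It gives only the chance of at least one event per 100 at those assumed rates.

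The adverse event form is not in the documents, so additional causality fields on it cannot be ruled out.

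There is also a masking objection to any remedy. Section 9.7 gives adverse event assessment to the Masked Assessor, who cannot attribute an event to heat, expression or compress without learning the arm. This is a fair point, and the fix has to allow for it.

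**Conclusion.** The point holds in a limited form. On the visible text, the first safety endpoint is 0 by construction in the control arm until crossover and cannot serve the comparative safety objective. This follows from the wording and needs no assumption about event rates.

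The size depends on rates that the plan does not give. At an equal true rate of 5% the displayed contrast would be an expected 5 versus 0 when the truth is 5 versus 5. That error works against TearCare; a narrow reading of the device boundary would work in its favour. The forceps issue is an ambiguity, not a demonstrated omission. The literal conflict of 10.1 and 12.1 with 12.5.9 is real and should be removed in the same edit.

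This should be changed, but it does not undermine the trial, because all-event comparison by arm remains available.

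**What to change.** 1. State in 4.3 or 10.1 whether the forceps and the expression step count as the study device.
2. On the adverse event form and in sections 10 and 10.3, record relatedness to the assigned study treatment (TearCare session, expression, or compress and massage) and to study tests. The Masked Assessor documents the event; an existing unmasked investigator assigns causality. Section 10.3 already makes the investigator responsible for recording the relationship. Amend 9.7 to match.
3. In 6.2, make study-treatment-related adverse events by arm the comparative endpoint, with device-related events as a sub-row. Keep the all-event tables of 12.5.9.
4. Extend the adverse event definition in 10.1 and the safety set in 12.1 to all treated subjects in both arms.

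The cost is a few extra form fields, wording changes in these sections, and a separate causality step to protect masking. The related-event count may rise in either arm.

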10.1 DEFINITIONS OF AE, SAE, SADE, USADE

Adverse Event	Any untoward medical occurrence in a subject who has been treated with the device that does not necessarily have causal relationship with the treatment.
Adverse Device Effect	Any unfavorable and unintended sign (including an abnormal laboratory finding), symptom, or disease that is possibly related to the study device.
Serious Adverse Event (SAE)	Any untoward medical occurrence that: Results in death Is life-threatening Requires in-patient hospitalization or prolongs existing hospitalization Necessitates medical or surgical intervention to preclude permanent impairment of a body function or permanent damage to a body structure Sight threatening
Unanticipated Adverse Device Effect	Any serious adverse effect on health or safety, any life-threatening problem or death caused by, or associated with a device if that effect, problem, or death was not previously identified in nature, severity, or degree of incidence in the clinical investigational plan; or any other serious problem associated with a device that relates to the rights, safety, or welfare of subjects (21 CFR 812.3(s)). Any sight-threatening event, whether listed in the protocol or not, is considered to be reportable as a UADE

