12.5.9 SAFETY ANALYSIS

All adverse events will be reported by treatment group and AE category. Any serious adverse events will be completely described in the study report.

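### The adverse event definition and the safety-evaluable set cover device-treated subjects only, which contradicts the plan's own assessment and reporting of adverse events in both arms

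*Combined protocol and SAP*

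**What the plan says.** The opening of protocol section 10 points to the definitions that follow it. Section 10.1 then defines an adverse event as "Any untoward medical occurrence in a subject who has been treated with the device that does not necessarily have causal relationship with the treatment". The limiting words are "in a subject who has been treated with the device". The serious adverse event entry in the same table begins "Any untoward medical occurrence that: Results in death Is life-threatening" and carries no condition about the device. The remaining two entries concern device effects.

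Two other places share the device-only wording. Section 12.1 treats a subject as evaluable for safety if TearCare was attempted. Section 10 and section 10.3 have the investigator record on the form how the event relates to the study device, and mention no rating of relationship to the control treatment.

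Controls first receive TearCare when they cross over after the 6 month visit (12.5.8; SAP, Appendix C, 23.1.6).

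Other sections treat adverse events as arising in both arms:

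- 6.2: "all adverse events will be recorded".
- 9.5.1: subjects randomized to warm compress have an adverse event assessment at the first visit.
- 9.6.1: adverse event assessment is part of the follow-up sequence, with no limit by arm.
- 9.7: that assessment belongs to the Masked Assessor.
- Section 10, opening: "Adverse events that occur in the eye during the trial, whether they are considered to be device related or not, must be documented".
- 10.2: anticipated events can arise from "study testing methods or potential risks associated with warm compresses and lid massage".
- 12.5.9: "All adverse events will be reported by treatment group and AE category".

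**The concern.** The stated objective is to show safety and effectiveness against daily warm compress and lid massage, in support of a new indication. A safety comparison needs the same rule for what counts as an event in each arm. As worded, the definition gives the control arm no way to have a non-serious adverse event during the first six months, and 12.1 gives it no place in the safety set over that time. A mild lid burn from a compress would fit no category in 10.1, although 10.2 anticipates it.

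The two gaps act at different stages. If 10.1 is followed literally, the event is not recorded, and a later change to the analysis set cannot recover it. If 12.1 is followed literally, the event may be in the database but its subject is outside the set. Separately, with relationship rated only to the device, an event caused by the compress can be marked only as unrelated to the device.

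**Working it through.** **The plan's own safety figures.** SAP section 23.2.3 gives three worked numbers for 100 subjects. All three reproduce:

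- Chance of at least one event at a true rate of 0.01: 1 − 0.99^100 = 0.634 (stated 0.634).
- One-sided 95% upper limit for 0/100, Wilson score with k = 1.645: k²/(n + k²) = 2.706/102.706 = 0.026 (stated 0.026).
- Same method for 1/100: 0.0436 (stated 0.044).

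Each describes one sample, so none depends on the arm comparison and none changes.

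**Who meets the wording, and when.**

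| Group and period | Adverse event under 10.1? | Safety-evaluable under 12.1? | Assessed or reported elsewhere? |
|---|---|---|---|
| TearCare, after the procedure | yes | yes | yes |
| TearCare, from randomization to a deferred procedure (up to 7 days, 9.5.1) | no | once attempted | recording under 6.2 and 10 |
| Control, baseline to crossover | no, unless serious | no | yes (6.2, 9.5.1, 9.6.1, 10.2, 12.5.9) |
| Control, after crossover | yes | yes | yes |

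The third row is the contradiction. It covers all 100 planned controls for about six months, including the 1 month primary time point.

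**Size if the wording is applied.** Inputs: 100 per arm (12.7); true rates 0.01, 0.02 and 0.05, the values used in 23.2.3; equal rates in both arms (assumption); and c, the fraction of control events captured (assumption, since no document gives it). Expected counts are 100 × p for TearCare and 100 × p × c for control. The artificial difference is p × (1 − c).

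| p | c = 1 | c = 0.5 | c = 0 | Artificial difference at c = 0.5 and c = 0 |
|---|---|---|---|---|
| 0.01 | 1 v 1 | 1 v 0.5 | 1 v 0 | 0.5 and 1 point |
| 0.02 | 2 v 2 | 2 v 1 | 2 v 0 | 1 and 2 points |
| 0.05 | 5 v 5 | 5 v 2.5 | 5 v 0 | 2.5 and 5 points |

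The plan names no test for adverse events. As a guide, Fisher's exact two-sided p is 0.059 for 5 v 0 and 0.029 for 6 v 0. With p = 0.05 and c = 0, the chance of 6 or more TearCare subjects with an event is 0.38. An empty control column would also carry the plan's own upper limit of 0.026, below the assumed true rate of 0.05.

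**Direction.** Every c below 1 removes control events only, so TearCare looks relatively worse.

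**The case against.** The strongest reply is that the operating procedures make the intent plain. Controls are assessed on the first day and at follow-up. The assessor is masked until all subjects at the site have passed 6 months and so cannot apply a rule that depends on arm. Ocular events are to be documented whether or not they relate to the device. Controls also complete the discomfort/pain questionnaire after the supervised session (9.5.5), and the slit lamp, visual acuity and pressure examinations in 9.6.1 are not limited by arm. Serious events fall outside the restriction, and the named safety endpoint in 6.2 is device-related events, which controls cannot have before crossover.

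Most of this stands. A reader might infer from 10.1 that the comparison of arms is already distorted and that compress harms are not captured. The documents do not support that: distortion requires someone to follow the definition against several explicit instructions. Nor do they support a reading that the wording favours the device, since the error would run the other way. Table 3 is not shown and the form is not included, so what sites were told in practice cannot be checked.

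What does not stand is that these passages settle the matter. Each relies on the term adverse event, and section 10 refers to 10.1 for its meaning. Being told to assess a control does not say what counts. Masking is a partial safeguard: 10.3 makes the principal investigator responsible for identifying, collecting and reporting events and for recording relationship to the device, and nothing requires that person to be masked. The recording rule at the start of section 10 covers ocular events only. None of these passages brings controls into the set in 12.1.

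**Conclusion.** The point holds as an internal contradiction that creates a risk. Section 10.1, section 12.1 and the relatedness item on the form are written for device-treated subjects, while 6.2, 9.5.1, 9.6.1, 10.2 and 12.5.9 require or presuppose adverse events in controls. The affected events are non-serious control events before crossover.

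At an assumed 5% rate in both arms of 100, the expected counts run from 5 v 5 through 5 v 2.5 to 5 v 0. The last is the extreme of literal use, not a forecast. The equal rates and the capture fractions are assumptions; the documents support only the arm sizes and the range of rates. With up to 15 centers, uneven reading between sites is plausible, and events not recorded at the time may be lost. The wording should be corrected.

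**What to change.** Make three changes together, since none suffices alone:

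1. **Section 10.1.** Define an adverse event as any untoward medical occurrence in an enrolled subject in either arm, from the first study procedure, whether or not it is related to the device or to the control treatment. Starting at randomization would be too late: baseline examinations come before it (9.5.1), and 10.2 counts study tests as a source of events.
2. **Section 12.1.** Make all randomized subjects who start either assigned treatment evaluable for safety, so that the report by treatment group in 12.5.9 has a denominator in both arms.
3. **Adverse event form (section 10 and 10.3).** Add a field for relationship to the assigned treatment, TearCare or warm compress/lid massage. Have it completed in a way that keeps the Masked Assessor masked.

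The cost is some rewording, one added form field and a few more control events to record. No sample size or precision figure changes.

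### The SAE definition in Section 10.1 has no criterion for an event that results in permanent harm, so a narrow class of lasting injuries would not be classed as serious

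*Combined protocol and SAP*

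**What the plan says.** The SAE row of the table in Section 10.1 has five criteria. Three are the usual ones: "Results in death Is life-threatening Requires in-patient hospitalization or prolongs existing hospitalization". The fourth is "Necessitates medical or surgical intervention to preclude permanent impairment of a body function or permanent damage to a body structure". The fifth is "Sight threatening".

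The UADE row of the same table is worded separately, cites 21 CFR 812.3(s) and does not refer to the SAE list. Its main part covers a serious effect "if that effect, problem, or death was not previously identified in nature, severity, or degree of incidence in the clinical investigational plan", and a second part covers other serious problems associated with a device. It ends with an automatic rule: "Any sight-threatening event, whether listed in the protocol or not, is considered to be reportable as a UADE".

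Two provisions depend on SAE status. Under Section 10.3, an ocular SAE "should be reported to the study sponsor within one working day of learning of the event", and a non-ocular SAE within two working days. Under Section 12.5.9, "Any serious adverse events will be completely described in the study report", while all adverse events are reported by treatment group and category.

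Section 10.2 lists "Burn, erythema, or swelling of the eyelids" among the anticipated events, with no limit on severity or duration.

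**The concern.** Read literally, the fourth criterion makes an injury serious when intervention was needed to stop it becoming permanent. The list says nothing about an injury that is permanent and did not call for such intervention. Averted harm can thus rank above realised harm.

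This bears on the present device because Section 11.6 names overheating of the eyelids first among the major risks and also mentions abrasion of the eyelid surface during gland expression. A lid injury that spares vision is not reached by the sight-threatening criterion. Safety is part of the study objective (Section 2). Section 12.8 plans no interim analyses, so prompt event reports are an important way for the sponsor to learn early of a lasting injury. TearCare subjects are re-treated at 6 months (Section 9.6.2), so late notice could follow further exposure.

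**Working it through.** No arithmetic applies. The check is to read the five criteria against two versions of one injury: a permanent, non-fatal eyelid injury that spares sight and needs no hospitalization. In case A it at no point necessitated intervention to prevent permanence. In case B it did.

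| Criterion in 10.1 | Case A | Case B |
|---|---|---|
| Death | no | no |
| Life-threatening | no | no |
| Hospitalization, new or prolonged | no | no |
| Intervention necessitated to preclude permanent harm | no | yes |
| Sight threatening | no | no |
| Criteria met | 0 of 5 | 1 of 5 |

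The next step is to see whether another provision would still treat case A as serious.

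1. *Ordinary adverse event reporting (Sections 10, 10.3, 12.5.9).* Case A is recorded with date, severity, treatment and relationship to the device, and counted by group and category. Section 10.3 sets no deadline to the sponsor for a non-serious event, and Section 12.5.9 promises full description only for SAEs.
2. *UADE, main part (Section 10.1).* The effect must be serious, a term not defined in that row, and not previously identified in nature, severity or degree of incidence. An investigator could argue that a permanent scar goes beyond the listed eyelid burn. Another could answer that eyelid burn is listed without a severity limit. Both readings fit the text.
3. *UADE, other serious problems.* This again turns on the undefined word serious, and needs an association with a device.
4. *UADE, automatic rule.* It covers sight-threatening events only, so it does not reach case A.
5. *Control arm.* Section 10.2 includes potential risks of warm compress and lid massage among the anticipated events. An injury from either alone is not associated with the device, so no part of the UADE definition that depends on the device applies.

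Case A therefore has no assured route to expedited reporting. If device-related, it has a possible one: Section 10.3 gives one working day to the sponsor for a UADE. If it arises from warm compress or massage alone, it has none.

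**The case against.** The strongest reply is that little falls through. The fourth criterion asks whether intervention was necessitated, not whether it was given. A burn that called for treatment to avoid a scar qualifies even if treatment was withheld or failed. Many permanent lid injuries would qualify that way. The rest remain visible: they are recorded and tabulated, the slit-lamp examination includes the eyelids (Section 21.3), monitors review charts (Section 13), and electronic entries are fully verified against source (Section 14.5). Some device-related cases would be reported as UADEs.

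All of this stands, and it narrows the point to case A. It does not close the gap. Routine recording and monitoring do not supply the SAE deadline or the full description, and the UADE route depends on individual judgement at up to 15 centers.

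A reader might also infer more than the documents support:

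- *That any permanent injury left untreated escapes the definition.* It does not, if intervention was needed.
- *That such an event is lost, or can have no sponsor deadline.* It is recorded, and the UADE route may apply.
- *That the SAE list decides what counts as a UADE.* The UADE row makes no reference to it.
- *That 1 to 5 of 100 TearCare subjects would be affected.* The proportions 0.01, 0.02 and 0.05 in Section 23.2.3 are illustrative inputs to a precision table for any adverse event, not lid-injury rates.
- *That lasting lid damage, rather than loss of sight, is the worst plausible result of overheating.* Section 11.6 does not say so.

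**Conclusion.** The concern holds in a narrow form. A permanent injury that does not threaten sight, does not lead to hospitalization and at no point necessitated intervention to prevent permanence meets 0 of 5 SAE criteria. For such an event the SAE classification, the one- or two-working-day sponsor report and the full description in the study report can be missed, although the event itself is still recorded and counted.

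The frequency cannot be sized. The documents give no rate for permanent lid injury. Section 10.2 calls the likelihood of the device's risk-analysis events remote, and both pilot studies (18 and 24 subjects, Sections 5.2.1 and 5.2.2) reported no adverse events. The events may be rare.

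The conclusion rests on reading the list as written and on the list being complete in the text available, which shows no sign of a lost item. Severity is minor.

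**What to change.** Add a sixth criterion to the SAE list in Section 10.1 for an event that *results in* permanent impairment or permanent damage, using the same terms for function and structure as the fourth criterion. Keep the five existing criteria.

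Align the adverse event form if it records seriousness. The form is not in the documents. Sections 10 and 10.3 name only date, severity, treatment and relationship as its contents, so whether it needs changing has to be checked.

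The cost is one line in the protocol, a possible form update, and perhaps a few more expedited reports. The analyses of effectiveness do not change.
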